Demographic Survey		•			
Ohio State Traumatic Brain Injury Identification Method-Short Form (OSU TBI-ID)		•			
Neurobehavioral Symptom Inventory (NSI)		•		•	•
Brief Symptom Inventory-18 (BSI-18)		•		•	•
Patient Health Questionnaire-9 (PHQ-9)		•		•	•
PTSD Checklist for DSM-5 (PCL5)		•		•	•
Coronavirus Anxiety Scale (CAS)		•		•	•
Applied Cognition-General Concerns-Short Form (ACGC-8a)		•		•	•
Applied Cognition-Abilities-Short Form (ACA-8a)		•		•	•
Hopkins Verbal Learning Test-Revised (HVLT-R)		•		•	•
Trail Making Test Parts A and B (TMT-A, TMT-B)		•		•	•
Wechsler Adult Intelligence Scale- Fourth Edition (WAIS-IV) Digit Span		•		•	•
Alcohol Use Disorders Identification Test (AUDIT)		•		•	•
Brief Addictions Monitor-Revised (BAM-R)		•		•	•
Pain Symptom Survey (PEG)		•		•	•
World Health Organization Quality of Life - BREF (WHOQOL-BREF)		•		•	•
General Self-Efficacy Scale (GSES)		•		•	•
Patient Global Impressions of Change (PGIC)				•	•
Client Satisfaction Questionnaire (CSQ)				•	•
Qualitative Interview				•	
Behavioral Health Measure-20 (BHM-20) Life Functioning Subscale			•		
Feasibility Metrics		•	•	•	•

Intervention. The test (E-PST) or control intervention will be administered to participants by a trained, therapist (Master's level-equivalent or higher). Psychological distress data (BHM-20 life-functioning subscale) will be collected during treatment sessions as part of routine outcome monitoring. Sessions will be audio-recorded for training and supervision purposes.

- **Test intervention (E-PST).** E-PST consists of 6, approximately 30-minute sessions focused on: a) reducing psychological distress by enhancing specific problem-solving skills; and b) developing specific cognitive and behavioral skills that target common cognitive inefficiencies reported in Veterans with mTBI history. The current therapist guide and participant workbook are included with this submission. We anticipate that sessions will be scheduled approximately biweekly but will afford flexibility in scheduling to aid in our assessment of feasibility of this planned approach.

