Primary analyses will focus on detecting post-treatment change in psychological distress as measured by the BSI-18's GSI T-score. We will test the preliminary hypothesis that E-PST (vs. control) will be associated with reduced psychological distress as measured by BSI-18. BSI-18 data will be described with means, standard deviations and CIs at each time point and condition. To show central tendency, variation and potential trends over time, means and 95% CIs will be plotted across time for each condition. Additional line plots connecting means across time will overlay the CIs to help illustrate trends. To assist in developing a larger trial, an ES will be calculated at post treatment to describe the standardized difference between conditions. The ES will be calculated by dividing the difference in the mean BSI-18 score between conditions at post-treatment by the pooled standard deviation. Then, the upper limit of a one-sided 80% CI under the null hypothesis of no difference between groups (ES = 0) will be compared to the observed ES by using the non-central *t*-distribution method discussed by Cumming & Finch (2001). We opted for a one-sided CI because we are interested in progressing toward a larger trial based on some evidence of effectiveness. The lower end of the CI is not informative in this pilot as the progression towards a larger trial would not occur even if the control condition was marginally more effective than E-PST. While a standard 95% CI provides greater coverage of the population difference, it also requires a larger sample of patients and associated increases in cost and time. Therefore, we propose an 80% interval that provides reasonable assurance of making the correct decision to move on to a larger trial (Cocks & Torgerson, 2013) While primary analyses focus on psychological distress, post-treatment ES's will also be calculated for secondary outcomes, and a correlation matrix will be built to describe the degree of correspondence among all outcomes. Our goal is to calculate a preliminary ES estimate that is representative of the true population using the ITT principle. Thus, all patients who are complete a baseline assessment and are randomized will be included in our analysis. We plan to utilize two sophisticated methods with the first being Maximum Likelihood Estimation (MLE), and Multiple Imputation (MI) as the second. A multi-level model (MLM) will be developed using MLE to calculate means and standard errors that will be used in the formation of an ES. MLM provides unbiased parameter estimates under a missing at random (MAR) assumption without resorting to listwise deletion of patients due to missing data. While the validity of MAR cannot be fully determined from the data, the reason for the missingness may depend on observed co-variates. If the latter case is true, MI (see below) is a viable and powerful option for imputing

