
missing values and satisfying the MAR assumption. We plan to conduct a sensitivity analysis to determine the effect of the missingness by comparing MI to MLE estimation via MLM.

Evaluation of feasibility will focus primarily on descriptive statistics. For instance, means and standard deviations will be calculated for time estimates for each primary and secondary measure and homework assignment. The study team will also record and review frequencies of completed vs. incomplete measures, and any relevant participant comments that pertain to lack of clarity or undue burden of measures. Recruitment over time will be displayed by plotting the cumulative number of patients enrolled into this study and compared to the anticipated rate of recruitment. Any intervention elements with relatively low fidelity will subsequently inform the future training curriculum that will be designed for EPST therapists in our full-scale RCT.

Qualitative feedback on experiences with E-PST (i.e., acceptability treatment satisfaction) and reasons for completion/ dropout will be analyzed via rapid qualitative analysis (Beebe, 2001). Rapid qualitative analysis will facilitate our ability to quickly incorporate patient feedback in planning our future RCT.

Phase 2 Sample Size Justification

a) *Quantitative Methods:* Using previously published ES data on the effect of PST in mTBI10 and the method described by Cocks and Torgerson (2013) we calculated the sample size to adequately employ an 80% one-sided CI to estimate the upper limit of the ES under the null hypothesis of no difference (ES=0) between conditions. The one-sided CI was calculated so that 32 patients allow for the upper limit of an 80% CI to exclude 0.3, or a difference of 0.3 standard deviations, between conditions. While 32 total participants are required to meet these parameters of CI estimation, we will seek to randomize a total of 38 Veterans to increase the precision of our estimate while accounting for the possibility of missed visits (see data attrition section below).

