b) *Qualitative Methods:* Diversity in opinion is paramount to promoting cultural and content validity, as well as comprehensibility of our newly-generated intervention. A sample of at least 12 is typically required to achieve saturation of opinions in qualitative work (Guest et al., 2006). Therefore, our maximum enrollment of 19 Veterans per group will provide an adequate mix of feedback and protect against loss of critical information due to attrition.

Phase 2 Data Attrition

Because E-PST is being adapted and initially tested over this line of funding, and delivered to a niche population of Veterans, we do not have a precise estimate of an expected level of attrition for this pilot trial. However, the evaluation of study feasibility, including that of recruitment and retention, is a core aspect of this pilot RCT. Therefore, data on participant dropout and missing data will be collected, analyzed, and figured into our plans for the future Merit application. As a point of reference, we calculated rates of attrition for recent intervention trials led by co-investigators and approximated 6% participant attrition over a 12-week window, and just 20% attrition over 6-months. Conservatively, the latter figure (20%) was selected as an expected upper limit of data attrition for planning the present pilot RCT. Because our proposed ITT analyses account for the possibility of missing data, we do not estimate that this will substantively hinder our analytic plan.

Phase 2 Plan to Address Missing Data

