We will use MI to manage missing quantitative data (Berglund & Heeringa, 2014). In order to predict missing values, regression models are used in the imputation process on existing data. The predicted values, called imputes, replace the missing values, thus resulting in a fully analyzable data set. This process is performed multiple times, resulting in many data sets; each data set is then analyzed to produce multiple sets of results. The results are then summarized to produce a single solution. The advantage of MI over other methods (e.g., last observation carried forward, mean substitution, expectation maximization) is that it preserves associations with other variables, adds variability during the imputation process, and accounts for variability due to multiple imputes, which results in efficient and unbiased parameter estimates (Berglund & Heeringa, 2014). Valid critiques of MI pertain to the variables used to fill-in the missing values, which may differ among analysts and can lead to biased parameter estimates (Kim et al., 2006). To address this criticism, we plan to use

VanBuuren's (2012) recommendations as well as practical guidelines in our imputation model. Our guideline encompasses inclusion of all items from the respective measure, variables that are correlated with the analysis variable, and variables that predict missingness.

References

Beebe, J. *Rapid Assessment Process: An Introduction*. AltaMira Press; 2001.

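### The only missing-data sensitivity analysis compares two methods that both assume MAR, so it cannot detect or bound dropout that depends on the unseen T2 BSI-18 score; a small delta-adjusted analysis would help

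*Combined protocol and SAP*

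**What the plan says.** Under Phase 2 Data Analysis, a) Quantitative Data Analysis, the primary ES is the T2 difference in mean BSI-18 score between conditions divided by the pooled SD. All randomized patients with a baseline assessment are included. Means and standard errors come from a multi-level model (MLM) fitted by maximum likelihood (MLE), of which the plan says: "MLM provides unbiased parameter estimates under a missing at random (MAR) assumption". It adds a caveat: "While the validity of MAR cannot be fully determined from the data". MI is then offered for the case where missingness depends on observed covariates, as a way to satisfy MAR. The one sensitivity analysis follows: a "sensitivity analysis to determine the effect of the missingness by comparing MI to MLE estimation via MLM".

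Phase 2 Plan to Address Missing Data builds the imputation model from the items of the measure, "variables that are correlated with the analysis variable, and variables that predict missingness". All of these are observed quantities.

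The observed ES is compared with "the upper limit of a one-sided 80% CI under the null hypothesis of no difference between groups", to inform the move to a larger trial. For attrition, Phase 2 Data Attrition reports that earlier trials "approximated 6% participant attrition over a 12-week window, and just 20% attrition over 6-months", and takes 20% as the expected upper limit. No section describes a delta-adjusted, pattern-mixture, selection-model, reference-based or tipping-point analysis.

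**The concern.** Two methods that share an assumption cannot test it. If MI and MLE differ, the likely reason is that the imputation model holds variables that the MLM lacks. If they agree, nothing follows about whether people with missing T2 scores differ from what their observed data predict.

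Take ES as control mean minus E-PST mean over the SD, so that positive values favour E-PST. The ES is overstated if missing E-PST scores are worse, or missing control scores better, than MAR predicts. It is understated in the reverse cases. Equal departures in both arms largely cancel when the missing fractions are similar. Estimating a preliminary ES is the first of the three stated Phase 2 goals. The 80% limit reflects sampling error only, so any such bias lies outside it.

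**Working it through.** **Inputs from the documents.** 19 randomized per arm, and 16 per arm sought with treatment data (Phase 2 Participants, Recruitment, and Enrollment); one-sided 80% limit under ES = 0 (Phase 2 Data Analysis); 0.3 SD (Phase 2 Sample Size Justification); attrition 6% and 20% (Phase 2 Data Attrition). The 6% figure is the closer guide to T2: six sessions about two weeks apart end near the 12-week point that Phase 1 Procedures gives as an example.

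**Assumed.** The departure from MAR (delta), because the documents give none; I use 0.25 to 1.0 SD of the T2 GSI T-score. I also assume that T3 and BHM-20 scores recover nothing.

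**1. The plan's own figure.** Per arm, n = 2 × (0.8416/0.3)² = 15.74, rounded up to 16, so 32 in total. The limit is then 0.8416 × √(2/16) = 0.298, which excludes 0.3. The stated 32 reproduces.

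**2. Null limit and standard error.** Limit = t(0.80, 2n−2) × √(2/n); SE = √(2/n).
- 19 per arm: SE 0.324; limit 0.8517 × 0.324 = 0.276.
- 15 per arm (19 × 0.80 = 15.2; complete-case approximation at 20% missing): SE 0.365; limit 0.8546 × 0.365 = 0.312.

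The 6% case keeps 19 per arm, since 0.06 × 19 is about one person.

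**3. Shift in ES from a departure in one arm.** Shift = missing fraction × delta.

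| Missing | 0.25 SD | 0.5 SD | 1.0 SD |
|---|---|---|---|
| 6% | 0.015 | 0.03 | 0.06 |
| 20% | 0.05 | 0.10 | 0.20 |

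Unequal missingness with the same 0.5 SD departure in both arms, for example 4 of 19 against 1 of 19, leaves (4/19 − 1/19) × 0.5 = 0.08.

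**4. Chance that the observed ES exceeds the limit.** This is 1 − F(limit/SE), where F is the noncentral t with 2n−2 df and noncentrality (true ES + shift)/SE.

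| Case | True ES | Shift | Without shift | With shift |
|---|---|---|---|---|
| 6%, 19 per arm | 0 | +0.03 | 20.0% | 22.7% |
| 6%, 19 per arm | 0.3 | −0.03 | 53.1% | 49.5% |
| 20%, 15 per arm | 0 | +0.10 | 20.0% | 28.5% |
| 20%, 15 per arm | 0.3 | −0.10 | 49.0% | 38.3% |

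**5. Chance that correcting a 0.5 SD one-arm departure changes the comparison.** Correcting an overstatement matters only if the observed ES lies just above the limit. Correcting an understatement matters only if it lies just below. The width is the shift from step 3.

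| Case | True ES | Just above | Just below |
|---|---|---|---|
| 6%, width 0.03 | 0 | 2.4% | 2.6% |
| 6%, width 0.03 | 0.3 | 3.6% | 3.6% |
| 20%, width 0.10 | 0 | 6.6% | 8.3% |
| 20%, width 0.10 | 0.3 | 10.5% | 10.7% |

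**6. Would the planned comparison show the problem?** A simulation with 19 per arm assumed a baseline–T2 correlation of 0.5 and 20% missing per arm. E-PST dropout rose with the unseen T2 score (logit slope 1.5 per SD), and control missingness was completely random. With true ES 0, MLE averaged 0.174 and MI 0.176, against −0.02 with complete data. The mean absolute gap between the two methods was 0.029. When data were truly MAR it was 0.029 to 0.031. The gap therefore carried no signal of a bias near 0.19, which is a deliberately unfavourable case.

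**The case against.** Read in sequence, the plan moves from possible dependence on observed covariates, to MI, to the comparison. On that reading the comparison was always a check within MAR, and only the stated purpose is loosely worded. That is fair on intent, but it leaves departures from MAR unexamined.

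Several features reduce the problem. Participants are encouraged to complete assessments after stopping treatment. T3 scores can inform the MLM. Session scores can inform the MI: "Psychological distress data (BHM-20 life-functioning subscale) will be collected during treatment sessions as part of routine outcome monitoring". The team will "record and review frequencies of completed vs. incomplete measures", and the T2 interview gathers reasons for dropout. These can lower the bias or help to interpret it, but none bounds it. The dropout reasons come from E-PST participants only, so they allow no comparison between arms.

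Sampling error also dominates: at 6% missing the shift is about a tenth of the standard error (0.03/0.324). The larger figures use a 6-month attrition rate adopted as an upper limit. Both points stand, and they keep the matter small.

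A reader might infer that an understated ES would wrongly stop the programme. The documents do not support this: no section says that falling short of the limit halts progression, and two of the three Phase 2 goals concern feasibility. A reader might also add the two columns of step 5 and quote roughly double the chance. A departure in a given direction can alter results on one side of the limit only.

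**Conclusion.** The concern holds in a limited form. The only planned missing-data sensitivity analysis stays within MAR, an assumption that the plan itself says cannot be fully determined from the data. It can therefore show the effect of auxiliary variables but not the full effect of missingness.

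Under an assumed 0.5 SD one-arm departure, the chance that correcting it would change the comparison is 2.4% to 3.6% in either direction at 6% missing, and 6.6% to 10.7% at 20%. These figures rest on the assumed delta, no recovery from T3 or BHM-20 scores, and the complete-case approximation at 20%.

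A reader might conclude that the ES will be biased or that the pilot is undermined. Neither follows: the documents give no evidence that dropout will depend on the outcome, and the ES is described as preliminary. This is a cheap improvement to consider.

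**What to change.** 1. Keep MI versus MLE, and describe it as a consistency check within MAR that shows the effect of auxiliary variables.
2. Prespecify a small delta-adjusted analysis on the planned MI. Shift imputed T2 GSI T-scores by ±0.25, ±0.5 and ±1.0 pooled observed T2 SD, in E-PST only and then in control only (6 × 2 = 12 scenarios).
3. Hold the null limit fixed at the n and df used for the primary ES comparison, and state both.
4. Report T2 BSI-18 missingness by arm, with the smallest delta in each direction, if any, at which the comparison with the one-sided 80% limit changes. Completion frequencies are already to be reviewed; the split by arm is the addition.

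The cost is a few lines of code and one table, with no new data or participants. With about 1 to 4 people missing per arm (0.06 × 19 = 1.1; 0.20 × 19 = 3.8), the result may be that no plausible delta matters. That would still be worth stating when planning the larger trial.
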